Primary analyses will be performed on an intent-to-treat basis that includes all randomized participants. Missing data could occur in several scenarios: (1) Loss to follow-up due to leaving employment, which is expected to have occurred at random in both groups and to be unrelated to the study outcomes; (2) Failure to attend a follow-up appointment or a visit to obtain a weight measurement; and (3) Censoring due to pregnancy. For participants who became pregnant during the intervention year, their follow-up values on all outcomes will be considered missing. We will impute missing data using multiple imputation and employing all available outcomes assessments and all prior data including baseline data, HEI conducted measured at 6 months, and all purchasing data prior to 2-year follow-up. We will conduct two sensitivity analyses: (1) including only participants who completed follow-up assessment at 1 year and (2) including only participants who remained employed at the hospital during the one-year intervention. If sensitivity analyses yield substantively different results, we will conduct exploratory analyses to assess reasons for the difference.

Hypothesis 1.1: The primary outcome is change in weight (kg) at the end of one year. Change in weight at the end of two years is a secondary outcome. Other secondary outcomes include *percent* body weight lost and gained less than 1 lb. We will compare the change in weight between intervention and control groups using a difference-in-

differences approach. To improve the precision of the effect estimate, we will use a linear/logistic regression analysis including age, sex, race, ethnicity, education, job type, and physical activity in the model.

We will use a repeated measures approach to combine data from 1-year and 2-year weight outcomes. A mixed effect model with a random effect for subject and a time treatment interaction will be used to examine the intervention effect at each time point and over the entire period.

Hypothesis 1.2: We will compare the changes in each of the cardiometabolic risk factors (waist circumference, systolic and diastolic blood pressure, fasting glucose, HbA1c, triglycerides, LDL and HDL cholesterol, total cholesterol) between intervention and control groups at the end of 1-year and 2-year follow-up using a difference-in-differences approach. The analysis strategy will be identical to the one used for the primary outcome in Hypothesis 1.1.

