Hypothesis 2.1: We will compare the healthfulness of food and beverages purchased at work between the intervention and control groups. Outcomes will include the average proportion of items purchased that are labeled green and labeled red, the average Healthy Purchasing Score, and the average number of calories of purchased foods during each one-year period (intervention period and follow-up period) compared to the baseline period (one year prior to enrollment). The analysis strategy will be identical to the one used for the primary outcome in Hypothesis 1.1.

Secondary analyses will explore the trend of these outcomes. We will explore whether the intervention effects diminish over time using a repeated measures approach. The mixed effect models will include a random effect for subject and a time treatment interaction fixed effect to determine whether the intervention effects differ among quarters or whether any trend exists.

Hypothesis 2.2: We will compare the change in dietary intake (via the Healthy Eating Index) of the intervention and control groups during the intervention year using 3 follow-up time points: 6 months, 1 year, and 2 years. We will utilize a mixed effects model that includes a random effect for subject and a time treatment interaction fixed effect to examine the intervention effect at the two time points separately. We will also add age, sex, race, ethnicity, education, and job type to the model to increase the precision of effect estimate.

VII. Risks and Discomforts

For all subjects, including the larger population of employees included in Aim 3 of the project, procedures to protect the privacy and to maintain confidentiality of data include the following: 1) Access to subject information will be protected by a Partners secure server. External access to such information is blocked by secure external firewalls. 2) Subjects will be assigned a unique study identification number. All data and the key linking the study identification number to the subject's information will be maintained on a Partners secure server that is password protected. 3) Identifiable study data will not be analyzed or published in any fashion that provides the ability to identify subjects.

[name] will screen all blood test results and will contact subjects individually to inform them of any critical results and to refer them for appropriate medical follow-up.

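### The 2019 mixed models for weight, quarterly purchases and HEI name only a random subject effect; stating a within-subject covariance would be a cheap improvement

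*Combined protocol and SAP*

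**What the plan says.** The Analysis Plan updated June 17, 2019 has three repeated-measures models.

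- **Weight (Hypothesis 1.1).** "We will use a repeated measures approach to combine data from 1-year and 2-year weight outcomes". The model is then given as "A mixed effect model with a random effect for subject and a time treatment interaction will be used to examine the intervention effect", both at each time point and over the whole period.
- **Purchases (Hypothesis 2.1, secondary analyses).** "We will explore whether the intervention effects diminish over time using a repeated measures approach". The specification is "The mixed effect models will include a random effect for subject and a time treatment interaction fixed effect", and the purpose is "to determine whether the intervention effects differ among quarters or whether any trend exists". The number of quarters and the form of time (linear or categorical) are not stated.
- **HEI (Hypothesis 2.2).** The comparison of change in diet is made "using 3 follow-up time points: 6 months, 1 year, and 2 years", with a "mixed effects model that includes a random effect for subject and a time treatment interaction fixed effect". The same sentence then speaks of only two time points.

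None of the three names a random slope, a residual covariance, visit-specific variances or a robust standard error. The plan names SAS 9.4 but no procedure. Protocol section VI says only that mixed effects or repeated measures analyses will be used.

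The primary 1-year weight comparison is a separate difference-in-differences regression. For the cardiometabolic outcomes and the yearly purchase outcomes the plan says: "The analysis strategy will be identical to the one used for the primary outcome in Hypothesis 1.1". That points to the regression and does not clearly place them in a mixed model.

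**The concern.** In its ordinary reading, a random subject effect means a random intercept with independent, equal-variance residuals. That is compound symmetry: one variance for all visits and one correlation for all pairs of visits. Weight change may well be more variable at 2 years than at 1, and adjacent quarters may well be more alike than distant ones. If so, the model's standard errors for single visits or for trends do not match the data.

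These models are asked the questions most sensitive to covariance: the effect at each visit, and whether it fades. HEI is the main exposure, because the mixed model is its only analysis in the 2019 plan, and Protocol section VI.B.2.c calls the 12-month HEI change primary.

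**Working it through.** **Inputs from the documents.** 270 per arm, two-sided 0.05, SD of 1-year weight change 5 lb (VI.A.1.d); SD of HEI change 15 points (VI.B.2.e). No 2-year weight SD, visit-specific HEI SDs or correlations are given. All of those below are assumptions, shown over a range.

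**1. The plan's own figures.** Weight: 1.5/(5 × √(2/270)) = 3.49, power 93.6% (stated 93%). HEI: 5/(15 × √(2/270)) = 3.87, power 97.2% (stated 97%). Both reproduce. They are two-sample calculations; no figure is stated for any mixed model.

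**2. Method.** With balanced, complete data, the random-intercept model estimates one variance (the mean of the visit variances) and one covariance (the mean of the pairwise covariances). For any contrast,

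type I error = 2Φ(−1.96 × √(model variance / true variance)).

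**3. Weight, two change scores, 1-year SD 5 lb.** Model variance = (25 + SD₂²)/2.

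| 2-year SD (lb) | Model variance | Error at 1 year | Error at 2 years |
|---|---|---|---|
| 4 | 20.5 | 7.6% | 2.7% |
| 5 | 25 | 5.0% | 5.0% |
| 6 | 30.5 | 3.0% | 7.1% |
| 8 | 44.5 | 0.9% | 10.2% |

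A simulation of 20,000 trials with SDs 5 and 7.07 lb gave 1.5% and 9.3%; the formula gives 1.6% and 9.0%. The average over visits is unaffected.

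**4. HEI change scores.** Model variance = mean of the visit variances.

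| Visits in model (months) | SDs | Model variance | 12-month error |
|---|---|---|---|
| 6, 12, 24 | equal | same as true | 5.0% |
| 6, 12, 24 | 13/15/17 | 227.7 | 4.9% |
| 6, 12, 24 | 14/16/14 | 216 | 7.2% |
| 6, 12, 24 | 16/14/16 | 236 | 3.2% |
| 6, 12 | 13/15 | 197 | 6.7% |
| 12, 24 | 15/17 | 257 | 3.6% |

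For SDs 13/15/17, the errors at 6 and 24 months are 2.3% and 8.2%.

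**5. If baseline is a response instead.** Take k follow-ups, equal change SD s and correlation r between changes. The residual variance is s²[k − (k−1)r]/(k+1); a visit's change has model variance twice that, and the average over visits has (1 + 1/k) times it. For weight at r = 0.7: 25 × 1.3/3 = 10.83. The visit has 21.67 against a true 25, and the average has 16.25 against 21.25.

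| r | Weight, per visit | Weight, average | HEI, per visit | HEI, average |
|---|---|---|---|---|
| 0.3 | 3.7% | 2.5% | 3.2% | 1.6% |
| 0.5 | 5.0% | 5.0% | 5.0% | 5.0% |
| 0.7 | 6.8% | 8.7% | 8.0% | 11.0% |

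**6. Quarterly purchases.** Assumed truth: subject variance 1 plus AR(1) residuals of variance 1 and correlation ρ. Example with 4 quarters and ρ = 0.5: mean residual correlation = (3 × 0.5 + 2 × 0.25 + 0.125)/6 = 0.354, so the model's residual variance is 0.646. For a linear slope (sum of squares 5), model variance = 0.646/5 = 0.129 against a true 0.1975. The true standard error is 1.24 times the model's, and the error is 11.3%.

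| Quarters | ρ | Arm-by-quarter test (omnibus) | Linear arm-by-time test | True/model SE, linear |
|---|---|---|---|---|
| 4 | 0.3 | 5.3% | 8.7% | 1.15 |
| 4 | 0.5 | 5.7% | 11.3% | 1.24 |
| 4 | 0.7 | 6.3% | 13.7% | 1.32 |
| 8 | 0.3 | 5.8% | 11.8% | 1.25 |
| 8 | 0.5 | 7.1% | 18.0% | 1.46 |
| 8 | 0.7 | 8.7% | 24.9% | 1.70 |

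The omnibus column comes from a weighted chi-square mixture (1,000,000 draws). Adjacent-quarter contrasts are conservative (1.9% to 3.4% over 4 quarters), and at ρ = −0.2 the linear test is too (3.0% over 4 quarters, 2.3% over 8).

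**The case against.** A reader might infer that the plan has committed itself to compound symmetry and that its standard errors are therefore wrong. The documents do not support that. In SAS a random subject effect can sit beside a structured residual or empirical standard errors, and nothing in the plan excludes this. The documents' single SDs imply no visit-specific error with change scores. Every departure from 5% above rests on an assumed SD or correlation, and the direction varies. This objection stands, and it limits the point to an improvement in specification.

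The text also favours change scores. The weight outcome is defined as change and the model combines the two follow-up years; the HEI model compares change over follow-up time points. The baseline-as-response figures, including those for the average effect, belong to the less natural reading, though the difference-in-differences wording leaves some doubt.

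The importance of HEI can be overstated. Its primary label is in Protocol VI.B.2.c; the 2019 plan names only 1-year weight change as the primary outcome. Protocol VI.B.2.d also gives a separate comparison at 1 and 2 years by the green-purchase method (two-sample t-tests), which has no covariance problem.

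The largest figures need 8 quarters, AR(1) correlation and a linear time term. The plan states none of these, and the analysis is exploratory.

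Finally, the figures assume complete data and no covariates, whereas the plan uses multiple imputation and adjustment. That affects their precision. It does not answer the point, because imputation deals with missing values and not with the covariance of the analysis model.

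**Conclusion.** The point holds as a cheap, worthwhile improvement and not as a demonstrated error. With change scores, visit-specific tests are correct if SDs are equal, and averages over visits are unaffected. With unequal SDs, the type I error at nominal 5% is 2.7% to 10.2% for 2-year weight (SD 4 to 8 lb) and 3.2% to 7.2% for 12-month HEI with three visits; the two-visit examples give 3.6% and 6.7%. If baseline is a response, the error also depends on the correlation between changes. For purchases with residual correlation decaying as AR(1) 0.3 to 0.7, the omnibus test is mildly anti-conservative (5.3–6.3% over 4 quarters, 5.8–8.7% over 8). A linear test, if used, is clearly so (8.7–13.7% and 11.8–24.9%).

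A reader might also infer that the trial's main result is at risk. It is not. The primary 1-year weight regression, its 93% power, the separate 2-year weight and yearly purchase regressions, and the cardiometabolic regressions are outside these models.

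**What to change.** - **Weight and HEI.** Replace the lone random subject effect with an unstructured within-subject covariance (PROC MIXED, REPEATED, TYPE=UN) over every follow-up visit in the model. State whether the response is the change score or includes baseline. Reconcile the three and two HEI time points in Hypothesis 2.2.
- **Quarterly purchases.** Use a random intercept and slope, or a serial residual structure, with empirical sandwich standard errors. State the number of quarters and whether time is linear or categorical.

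**Cost.** Plan wording and a few lines of SAS. With change scores, unstructured covariance needs 3 parameters for weight and 6 for three HEI visits, against about 540 participants. Eight quarters would need 36, hence the leaner structure there. Intervals widen where the current ones would be falsely narrow: the linear trend by about 15–32% over 4 quarters and 25–70% over 8 at the assumed correlations, and 2-year weight by 9–20% if its SD is 6–8 lb. If that SD is 4 lb, the 2-year weight interval is about 12% narrower.

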difference in the change from baseline to 1 year and from baseline to 2 years. The known predictors of weight change will also be included in the mixed effects models to improve the precision of parameter estimates.

d. Power calculation: A total of 670 subjects will be recruited. From a previous study,⁹⁰ we expect a <10% attrition rate and we do not expect the attrition rate to be different between the two study groups since change of employment was the main reason for loss-to-follow-up in our prior study. The final sample size for analysis will be 540, or approximately 270 per group. Using the data from our prior worksite exercise and nutrition studies, we estimate the standard deviation in weight change at 1 year is about 5 pounds. With 270 subjects per arm, the study will have 93% power to detect a mean difference as small as 1.5 lbs between the two study arms with a two-sided significance level of 0.05.

2. Hypothesis 1.2: Employees in the intervention group will have lower cholesterol, blood pressure, and hemoglobin A1c than the control group at 1 year and 2-year follow-up.

a. Outcomes: Outcomes will be change in total cholesterol, blood pressure, and HbA1c at 1 year and 2 years follow-up compared to baseline. Secondary outcomes will be change in waist circumference, LDL cholesterol, triglycerides, and glucose at 1 year and 2 years compared to baseline.

b. Analysis: We will compare the changes in the primary and secondary outcomes between intervention and control groups at the end of 1-year and 2-year follow-up using two-sample t-tests or Wilcoxon rank sum tests, whichever more appropriate. We will also use repeated measures analyses to combine data from both time points using mixed effects models. A time-treatment interaction term will be included in the models. We will evaluate 1) the overall average treatment effect across 1 year and 2 years and 2) the treatment group difference in the change from baseline to 1 year and from baseline to 2 years. The known predictors of outcomes will also be included in the mixed effects models to improve the precision of parameter estimates.

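### Efficiency only: the SAP's precision-adjusted regressions of change do not list the outcome's own baseline value, which is already collected; adding it cannot hurt in large samples and may help the secondary outcomes

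*Combined protocol and SAP*

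**What the plan says.** **Regressions of change.** Under Hypothesis 1.1, the Analysis Plan updated June 17, 2019 compares weight change between arms by difference-in-differences. For precision it fits a "linear/logistic regression analysis including age, sex, race, ethnicity, education, job type, and physical activity in the model". Hypothesis 1.2 compares changes in the cardiometabolic factors "between intervention and control groups at the end of 1-year and 2-year follow-up using a difference-in-differences approach". Hypotheses 1.2 and 2.1 both take over this method: "The analysis strategy will be identical to the one used for the primary outcome in Hypothesis 1.1". The list of seven covariates does not contain the baseline value of the outcome.

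**Mixed models.** For weight: "A mixed effect model with a random effect for subject and a time treatment interaction will be used". For quarterly purchases: "The mixed effect models will include a random effect for subject and a time treatment interaction fixed effect". For the Healthy Eating Index (HEI): "We will utilize a mixed effects model that includes a random effect for subject and a time treatment interaction fixed effect", with a covariate list of its own ("We will also add age, sex, race, ethnicity, education, and job type to the model to increase the precision of effect estimate") that does not name baseline HEI. None of these sentences says whether baseline is subtracted, is a row of the response, or is a covariate.

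**Older protocol text.** Section VI.A.2.b says "The known predictors of outcomes will also be included in the mixed effects models to improve the precision of parameter estimates", and VI.A.1.c has a parallel sentence for weight. The predictors are not named. Section VI.B.1.d adjusts purchases only for variables found to be out of balance.

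**The concern.** A comparison of changes amounts to fixing the slope of follow-up on baseline at 1. If the true slope differs from 1, the change score still carries variation that baseline could explain. Baseline is often among the stronger predictors of change because of regression to the mean. The SAP adjusts expressly to gain precision, and the list omits a natural candidate that the trial already holds.

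What is at stake is the width of the confidence intervals and the power for secondary outcomes. The validity of the trial is not at stake.

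**Working it through.** **Inputs from the documents.** 270 per arm, two-sided 0.05 (VI.A.1.d); 1:1 allocation (IV.B). Difference / SD of change: weight 1.5/5 lb (VI.A.1.d); total cholesterol 8.4/30 mg/dL, blood pressure 2.8/10 mmHg, HbA1c 0.28/1 (VI.A.2.c); green purchases 5/20 percentage points (VI.B.1.e); HEI 5/15 (VI.B.2.e).

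**Assumed, not in the documents.**
- ρ: baseline-to-follow-up correlation left after the listed covariates.
- k: SD at follow-up divided by SD at baseline.
- R²: share of change variance that the listed covariates already explain.

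**Step 1: reproduce the plan** (noncentral t, no adjustment). Weight 93.6% (stated 93%); cholesterol, blood pressure and HbA1c 90.1% each (90%); green purchases 82.6% (82%); HEI 97.2% (97%). All agree.

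**Step 2: variance with baseline added.** With equal variances σ², the change has variance 2σ²(1 − ρ) and the baseline-adjusted residual σ²(1 − ρ²). The ratio is (1 + ρ)/2, a cut of (1 − ρ)/2: 35/25/15/5% at ρ = 0.3/0.5/0.7/0.9. In general the ratio is k²(1 − ρ²)/(1 + k² − 2kρ), which is never above 1 and equals 1 only when the slope kρ is 1.

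**Step 3: cholesterol, blood pressure and HbA1c.** All three have difference/SD = 0.28. The noncentrality is 0.28/√(2/270) = 3.25; at ρ = 0.5 it becomes 3.25/√0.75 = 3.76. With k = 1:

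| Setting | SAP model | ρ 0.3 | ρ 0.5 | ρ 0.7 | ρ 0.9 |
|---|---|---|---|---|---|
| 270 per arm, R² 0 | 90.1% | 98.1% | 96.3% | 94.1% | 91.5% |
| gain, points | | 8.0 | 6.2 | 4.0 | 1.4 |
| 270 per arm, R² 20%, gain | 95.3% | 4.2 | 3.5 | 2.3 | 0.9 |
| 301 per arm, R² 0, gain | 92.9% | 6.0 | 4.8 | 3.2 | 1.1 |
| 301 per arm, R² 20%, gain | 97.0% | 2.8 | 2.4 | 1.7 | 0.6 |

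The 301 rows are there because VI.A.1.d also gives 670 recruited with under 10% attrition: 670 × 0.9 = 603, or about 301 per arm. At ρ = 0.5, R² 0 and 270 per arm, the cholesterol difference detectable with 90% power falls from 8.4 to 8.4 × √0.75 = 7.3 mg/dL.

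**Step 4: unequal SDs (270 per arm).** With k = 0.9 or 1.1 the variance cut runs from 0% to 42% and the gain from 0.0 to 8.8 points. The top is k = 0.9, ρ = 0.3, R² 0. The bottom is k = 1.1, ρ = 0.9, where the slope is 0.99 and the change score is already close to optimal.

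**Step 5: other outcomes (270 per arm, k = 1).**
- Weight, assumed ρ 0.95 to 0.98: +0.5 to +0.2 points at R² 0; +0.3 to +0.1 at R² 20%.
- Green purchases, R² 0: +9.1/5.6/1.9 points at ρ 0.5/0.7/0.9. This is illustrative: the planning SD belongs to a monthly proportion, and the SAP now averages over a year.
- HEI, R² 0: +2.6/2.2/1.6/0.6 points at ρ 0.3/0.5/0.7/0.9, and only if baseline is subtracted or entered as a response row with free arm means. In a random-intercept model, either gives a standard error of 15 × √(2/270) = 1.291 for the 12-month effect. Baseline as a by-visit covariate, or arm means constrained equal at baseline, gives 1.041/1.118/1.190/1.258.

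**Step 6: validity.** In simulation on the blood pressure scale (4,000 trials per setting, ρ 0.5, 0.7, 0.95), type I error was 4.9–5.3% for the change score and 4.8–5.4% with baseline added. Both were unbiased for a true difference of 2.8. Variance ratios were 0.74–0.75, 0.85–0.86 and 0.98, against 0.75, 0.85 and 0.975 from the formula.

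**The case against.** The strongest reply is that nothing is broken. Comparing change is valid under randomisation, is pre-specified, and matches outcomes defined as change. The trial is sized on weight, where the gain is at most half a point. The larger gains fall on secondary-aim outcomes already planned at 82% to 97% power. They rest on ρ, k and R², none of which the documents give, and the range includes zero. All of this stands, which is why the point is one of efficiency.

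The mixed models also deserve care. A reader might infer that the SAP leaves baseline out of them. The text does not show that. The seven-covariate list belongs to the regression sentence, and the weight mixed model has no list of its own. The older protocol sentences on known predictors may therefore still apply to the weight and cardiometabolic mixed models, and a baseline value could be one of them. For these models the wording is unstated; an omission is not demonstrated.

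Finally, the SAP's past-tense wording on missing data suggests, without proving, that follow-up was well advanced by June 2019. A change of model then needs a date and blinding to results.

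The objection does not remove the narrower fact. The regressions of change carry an explicit list chosen for precision, and the baseline value is not on it.

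**Conclusion.** The point holds as an efficiency improvement to the regressions of change for Hypotheses 1.1, 1.2 and 2.1. The plan is valid as written. The algebra is certain; the benefit in this trial is not, because ρ, k and R² are assumptions.

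For total cholesterol, blood pressure and HbA1c the gain at 270 per arm lies between 0.0 and 8.8 points of power over the whole grid, and it is smaller if about 603 are analysed. The same algebra covers purchases and the other continuous cardiometabolic outcomes, so the benefit is not confined to those three. For weight it is negligible, and for HEI it is at most 2.6 points under the assumptions above. The binary weight outcome is outside this point.

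Two stronger readings should be resisted. One is that the effect estimates would be biased or the tests invalid; randomisation and the simulation speak against it. The other is that the trial is underpowered without this adjustment; the plan's own powers reproduce without any adjustment at all.

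**What to change.** In a dated SAP amendment made before any unblinded analysis, state that each continuous-outcome model includes the baseline value of that outcome in addition to the listed covariates: baseline weight for percent weight change, and the baseline-year average for purchases. The treatment effect stays on the change scale, because once baseline is in the model, regressing change or follow-up gives the same treatment coefficient.

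As a clarification, say how baseline enters the weight, cardiometabolic, quarterly purchase and HEI mixed models. Either use baseline and baseline-by-visit terms, or treat baseline as a response with arm means constrained equal. The two are equivalent under the equal variances that a random-intercept model assumes.

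The cost is the amendment wording and one degree of freedom per visit. No new data are needed: baseline values are collected, and the SAP already uses them in the multiple imputation.
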